2.2 Analysis sets

All below defined analysis sets will be used to analyze data from both the selection phase (part 1) and the expansion phase (part 2).

Full Analysis Set

The Full Analysis Set (FAS) comprises all subjects to whom study treatment has been assigned by randomization. According to the intent to treat principle, subjects will be analyzed according to the treatment they have been assigned to during the randomization procedure regardless of whether or not treatment was administered. This population will be the primary population for efficacy analysis.

Per protocol set (PPS)

Not applicable.

Safety

The Safety Set includes all subjects who received at least one dose of study treatment. Subjects will be analyzed according to the study treatment received, where treatment received is defined as the randomized treatment if the subject took at least one dose of that treatment or the first treatment received if the randomized treatment was never received.

The actual treatment received corresponds to:

- the randomized treatment if patients took at least one dose of that treatment.
- the first treatment received if the randomized treatment was never received

Note: if a patient is assigned to a dose level for instance, PDR001 400 mg and just receives partial infusion of the treatment, the patient will still be analyzed under PDR001 400 mg treatment arm for safety analysis.

Biomarker analysis set

The biomarker analysis set, as it pertains to the secondary objective (Section 10.5.5 of the protocol), consists of all subjects in the safety set with an evaluable baseline tumor biopsy sample and at least one evaluable post-baseline tumor biopsy sample. [REDACTED]

Immunogenicity (IG) analysis sets

The *Immunogenicity prevalence set* includes all subjects in the Full analysis set with a determinant baseline IG sample **or** at least one determinant post-baseline IG sample.

The *Immunogenicity incidence set* includes all subjects in the Immunogenicity prevalence set with a determinant baseline IG sample **and** at least one determinant post-baseline IG sample.

See [Section 2.10.1.1](#) for the definition of *determinant*.

Patient Classification:

Patients may be excluded from the analysis populations defined above based on the protocol deviations entered in the database and/or on specific subject classification rules defined in [Table 2-4](#).

Table 2-4 Subject classification based on protocol deviations and non-PD criteria

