Analysis set	Protocol deviations leading to exclusion	Non protocol deviation leading to exclusion
FAS	No written inform consent	Not applicable
Safety set	No written inform consent	No dose of study medication
Biomarker set	No written inform consent	No dose of study medication and no evaluable post-

		baseline tumor biopsy sample
Immunogenicity Prevalence Set	No written informed consent	Not meeting the definition for inclusion in the Immunogenicity Prevalence set
Immunogenicity Incidence Set	No written informed consent	Not meeting the definition for inclusion in the Immunogenicity Incidence set

Withdrawal of Informed Consent

Any data collected in the clinical database after a subject withdraws informed consent from all further participation in the trial, will not be included in the analysis. The date on which a patient withdraws full consent is recorded in the eCRF.

Death events may be used in the analysis if captured from public records (registers), local law and subject informed consent pending.

Additional data for which there is a separate informed consent, e.g. [REDACTED] biomarker etc., collected in the clinical database without having obtained that consent will not be included in the analysis. These data will be excluded by the presence of the appropriate protocol deviation criterion.

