2.12.3 Biomarker data

As a project standard, Novartis Oncology Biostatistics will analyze only biomarkers collected in the clinical database. The biomarker analysis covered within the SAP pertains mainly to the secondary objective endpoint of determining the proportion of subjects with a favorable biomarker profile (pFBP, Table 1-1 and Table 2-18).

The biomarker analysis set, as it pertains to the secondary objectives (Table 1-1) as well as the analysis of the change in LAG-3 expression levels, consists of all subjects in the safety set with an evaluable baseline tumor biopsy sample and at least one evaluable post-baseline tumor biopsy sample.

Table 2-19 summarizes the biomarker collection schedules and sample types which are in scope with this SAP.

Table 2-19 Sample biomarker summary table

Biomarker parameter	Biomarker analysis measurement	Time point	Sample	Method	Dataset
Number of TILs	Percent of tumoral CD8 ⁺ cells	Screening Btw, C1D1 and C2D1*	Newly obtained tumor biopsy	IHC	B1

Biomarker parameter	Biomarker analysis measurement	Time point	Sample	Method	Dataset
Activation level of TILs	Percent of tumoral GzmB+ within CD8+cells	Screening Btw, C1D1 and C2D1*	Newly obtained tumor biopsy	FIHC/AQUA	B1
Activation level of TILs	Percent of tumoral CD8+ within Ki67+ cells	Screening Btw, C1D1 and C2D1*	Newly obtained tumor biopsy	FIHC/AQUA	B1
TIL repertoire/ specificity of T cell response to tumor	TCR clonality	Screening Btw, C1D1 and C2D1*	Newly obtained tumor biopsy	TCR sequencing	B1
Changes in immune response gene expression signatures	Gene signature expression levels	Screening Btw, C1D1 and C2D1*	Newly obtained tumor biopsy	Nanostring	B1

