2.12.4 General data handling and preprocessing

The mean of all pre dose assessments (i.e. screening and Cycle 1 Day 1 assessments) will be used as the baseline value. The on-treatment assessment will be the result from the tumor biopsy taken between C1D21 and C2D1.

When more than one biomarker data value are available for a subject at any time point, the mean of the replicate values will be used for all statistical analyses.

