- As for the activation level of TIL, an increase from baseline to on-treatment in percentage of GzmB+ T cells is considered favorable. In the presence or absence of an increase in GzmB+ T cells, an increase in percentage of Ki67+ T cells is also considered favorable. If decreases in both GzmB + T cells and Ki67+ T cell are observed, this parameter would not be considered favorable.

- As for the TIL repertoire/specificity of T cell response to tumor, an increase from baseline to on-treatment in TCR clonality is considered favorable.
- An increase from baseline to on-treatment in the aggregate gene signature score would be considered favorable.

For each biomarker involved in the evaluation of pFBP as stated above, the baseline, 3-4 weeks biomarker values, and the difference from baseline to 3-4 weeks will be listed for each individual patient by combination arm. The mean, standard deviation, %CV, median, minimum, maximum, inter-quartile range and number for all patients (regardless of treatment arms) will be reported for baseline and change from baseline to 3-4 weeks by combination arm. Inter-quartile range is the number of data points between the 25th and 75th percentile.

If an individual subject has two or more favorable biomarker parameters from [Table 2-16](#) then that subject will be considered to have a favorable biomarker profile.

For each combination arm, the proportion of subjects with a favorable biomarker profile (pFBP) are then defined as the number of subjects with favorable biomarker profiles divided by the number of subjects enrolled into the arm which are included in the biomarker analysis set for that particular interim analysis and will be summarized.

[REDACTED]

[REDACTED]

[REDACTED]

[REDACTED]

[REDACTED]

[REDACTED]

[REDACTED]

[REDACTED]

[REDACTED]

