2.2 Analysis sets

All below defined analysis sets will be used to analyze data from both the selection (Part 1) and expansion (Part 2) phases. Note, the immunogenicity (IG) analysis sets are outside the scope of the interim analyses (IA).

Full Analysis Set

The Full Analysis Set (FAS) comprises all subjects who received at least one dose of study treatment. This population will be the primary population for efficacy analysis.

Safety

The Safety Set is identical to the FAS.

Note: Even if the subject receives partial infusion of the treatment or only one component of the treatment, the subject will still be analyzed under PDR001+LAG525 treatment arm.

Biomarker analysis set

The biomarker analysis set, as it pertains to the secondary objective (Section 10.5.5 of the protocol), consists of all subjects in the safety set with an evaluable baseline tumor biopsy sample and at least one evaluable post-baseline tumor biopsy sample.

Evaluability for the analysis of the secondary objective will consist of the following:

- Having both tumor biopsy samples as stated above,
- Having quantifiable results for at least two assays to calculate the secondary endpoint as described in [Section 2.12.2](#).

Immunogenicity (IG) analysis sets

The immunogenicity prevalence set includes all subjects in the Full analysis set with a determinant baseline IG sample **or** at least one determinant post-baseline IG sample.

The immunogenicity incidence set includes all subjects in the Immunogenicity prevalence set with a determinant baseline IG sample **and** at least one determinant post-baseline IG sample.

See Section 2.10.1.1 of the main SAP for the randomized part of the study for the definition of determinant.

For more information on the additional analyses sets as well as subject classification and withdrawal of informed consent information, see the main SAP for the randomized part of the study.

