2.12.2 Secondary biomarker objectives

Changes in phenotype and/or activation of T cell populations in the tumor and tumor microenvironment will be analyzed on an on-going basis as part of the secondary objective. Every effort will be made to make this data available for internal decision making purposes. Such analyses may include, but are not limited to number of CD8⁺ T cell infiltration, T cell activation level by IHC and gene expression analysis. T cell repertoire/clonality by TCR-sequencing is excluded from all interim analyses as well as beyond due to low assay success. Further discussions of the parameter definitions to support the biomarker objectives can be found in [Table 2-3](#) below.

Table 2-3 Parameter definitions for categorization of biomarker outcome at subject level

Biomarker parameter	Analysis	Criteria for favorable biomarker result
Number of tumor infiltrating T cells (TILs)	Changes of CD8 ⁺ T cell numbers as assessed by IHC in tumor/ tumor microenvironment with treatment	Increase
Activation level of TILs*	Change of T cell activation marker level(s) as assessed by IHC in tumor/tumor microenvironment with treatment	Increase
Changes in immune response gene expression signatures	Changes in expression of genes and/or gene signatures as assessed by mRNA analysis in tumor/tumor microenvironment with treatment	Defined per gene/gene signature

*Of note, the activation level of TILs by IHC (AQUA analysis) initially reported in the protocol may be excluded due to sample limitation associations with arm 1A, created by the need to retain tissue for potential further LAG3 test validation in support of future diagnostic development.

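### Main SAP: a subject with results for fewer than two biomarker parameters stays in the pFBP denominator but cannot count as favorable, so assay failure lowers the reported proportion.

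*SAP*

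**What the plan says.** **Numerator (main SAP 2.12.5.3, calculation of the proportion with a favorable profile).** "If an individual subject has two or more favorable biomarker parameters from" the parameter table, that subject has a favorable profile. The cross-reference there is to Table 2-16; the four parameters (CD8 count, T-cell activation, TCR clonality, gene signatures) are in Table 2-18.

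**Denominator (same section).** The count of favorable subjects is "divided by the number of subjects enrolled into the arm which are included in the biomarker analysis set".

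**Biomarker analysis set.** Main SAP 2.12.3 says that it "consists of all subjects in the safety set with an evaluable baseline tumor biopsy sample and at least one evaluable post-baseline tumor biopsy sample". Section 2.2 gives the same sample-level definition, ending with "at least one evaluable post-baseline tumor biopsy sample", and a redaction follows. Neither visible text asks for a minimum number of parameters with results, and none says how a missing parameter is scored.

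**Table 2-4 (main SAP 2.2).** The non-deviation ground for exclusion from the biomarker set begins "No dose of study medication and no evaluable post" and goes on to the post-baseline biopsy. It joins the two conditions with a conjunction and does not mention the baseline biopsy.

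**Arm 1A SAP, same endpoint.** Its section 2.2 keeps the biopsy requirement and adds a separate condition: "Having quantifiable results for at least two assays to calculate the secondary endpoint". Its 2.12.3 calls the result the paired biomarker analysis set, and its 2.12.5.3 uses that set as the pFBP denominator. Its 2.12.2 also says that TCR sequencing is "excluded from all interim analyses as well as beyond due to low assay success".

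**The concern.** The numerator rule works on parameters and the denominator rule works on biopsies. The two agree only if every evaluable biopsy pair gives results for at least two parameters. Neither SAP expects assays always to work: main SAP 2.12.1 foresees sample and assay problems that preclude analysis, and the Arm 1A SAP later drops one of the four parameters because the assay too often failed.

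Where an assay fails, the subject is scored as if the tumor had shown no favorable change. pFBP then mixes the treatment's biological effect with tissue yield. It is a listed secondary endpoint, and main SAP 1.1.1 and 2.5.2 let biomarker data be considered alongside ORR when an arm is expanded, continued or dropped. The first look comes at about 10 subjects per arm, where one or two failed assays visibly move a proportion.

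**Working it through.** The SAP states no pFBP value, assumed rate or assay success rate, so there is no figure to reproduce. The check is a logical identity followed by an illustration.

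**Step 1: the identity.** Let q be the share of the set with results for 0 or 1 parameters. These subjects have probability 0 of two favorable parameters. Hence

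reported pFBP = (1 − q) × pFBP among subjects with two or more parameters.

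Example with assumed counts: 30 subjects in the set, 6 with fewer than two parameters, 12 favorable. The main SAP gives 12/30 = 40%; the restricted denominator gives 12/24 = 50%. Here q = 6/30 = 20%, and 0.80 × 50% = 40%.

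**Step 2: chance of a favorable profile by number of parameters.** Assume that each available parameter is favorable with probability p, independently. With k parameters the chance is P(Bin(k, p) ≥ 2):

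| k | 0 | 1 | 2 | 3 | 4 |
|---|---|---|---|---|---|
| p = 0.5 | 0 | 0 | 0.25 | 0.50 | 0.69 |
| p = 0.7 | 0 | 0 | 0.49 | 0.784 | 0.916 |

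**Step 3: size under assumed assay success.** Success rates for CD8, activation, TCR and gene signature are assumed and independent; p = 0.7. For the first row:

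- P(0 results) = 0.1 × 0.4 × 0.6 × 0.3 = 0.0072.
- P(1 result) = 0.0648 + 0.0108 + 0.0048 + 0.0168 = 0.0972, so q = 0.1044.
- P(2, 3, 4 results) = 0.3352, 0.4092, 0.1512.
- Reported pFBP = 0.3352 × 0.49 + 0.4092 × 0.784 + 0.1512 × 0.916 = 0.624.
- Restricted pFBP = 0.624 / (1 − 0.1044) = 0.696.

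The other rows follow in the same way:

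| Assumed success | q | Main SAP denominator | Two or more parameters | Difference |
|---|---|---|---|---|
| 0.9 / 0.6 / 0.4 / 0.7 | 10.4% | 62.4% | 69.6% | 7 points |
| 0.8 / 0.5 / 0.2 / 0.6 | 24.8% | 47.2% | 62.8% | 16 points |
| 0.95 / 0.85 / 0.7 / 0.85 | 1.1% | 80.7% | 81.6% | 1 point |

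**Step 4: what the restriction leaves.** With all four parameters available, the same model gives 91.6%. The restricted denominator reaches only 69.6% or 62.8% in the first two rows, because a subject with two or three parameters has fewer chances to reach two than a subject with four. The restriction removes the structural zeros but not the whole dependence on assay yield.

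**The case against.** **The redaction.** In the Arm 1A SAP, the sentence defining the set is followed by a definition of evaluability that includes the two-assay rule. In the main SAP the text at that same point is blacked out, and the section refers to a protocol section that is not shown. A hidden rule is possible, so the point is limited to the visible text. It is still worth making: main SAP 2.12.3 restates the set for the secondary objectives with no two-assay condition, and the Arm 1A SAP lists the rule beside the biopsy requirement, as something that an evaluable biopsy does not already imply.

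**Missing as unfavorable is a recognised convention.** Main SAP 2.5.3 uses it for ORR. There, however, it is stated. For pFBP nothing visible says that it was chosen.

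**Stronger readings that a reader might infer, and that the documents do not support:**

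- *Treated subjects without paired tissue enter pFBP through Table 2-4.* Sections 2.2 and 2.12.3 both require baseline and post-baseline biopsies. The table wording contradicts them and needs correcting, but it does not show that such subjects would be counted.
- *Subjects with no result at all, or biopsied only outside the window, are a material part of the problem.* Section 2.12.4 says: "The on-treatment assessment will be the result from the tumor biopsy taken between C1D21 and C2D1". A subject with an evaluable biopsy only outside that window is conceivable, but Table 2-19 lists just screening and one on-treatment sample. A pair with no result on any assay would hardly be called evaluable. The firm case is the subject with one parameter.
- *The denominator explains why pFBP is not comparable with Arm 1A.* Arm 1A also uses minimum sizes of change and fewer parameters, so the values would differ under identical denominators.
- *Arm selection is distorted.* Table 2-9 uses ORR only, section 2.5.2 makes ORR the primary basis, and no pFBP threshold or test is specified. Subject-level values and the number per biomarker are already reported, so attentive readers could see assay loss.

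**Conclusion.** The point holds on the visible main SAP text. A subject with results for fewer than two parameters is scored as not favorable because of assay failure, and reported pFBP is lowered by the factor (1 − q). That factor is exact. Its size is unknown: about 1 to 16 points in the illustrations, all of which rest on assumed success rates, an assumed 70% chance of a favorable result per parameter, and independence between assays that share the same biopsies. The effect is confined to a descriptive secondary endpoint that supports arm decisions; the ORR rules and the primary test are untouched.

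**What to change.** In main SAP 2.2, 2.12.3 and 2.12.5.3, define the pFBP denominator as treated subjects with baseline and on-treatment results for at least two of the Table 2-18 parameters, in the manner of the Arm 1A paired set. If the redacted text already contains such a rule, repeat it in 2.12.3 and 2.12.5.3.

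Report by arm the number of subjects excluded by this rule and the distribution of evaluable parameters per subject. This is needed because the restriction does not equalise subjects with two, three and four parameters.

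Reword the Table 2-4 entry so that any one of these excludes: no dose, no evaluable baseline biopsy, or no evaluable post-baseline biopsy.

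The cost is SAP wording, one derived flag and one small table. The denominator becomes somewhat smaller, and its precision falls accordingly. The change does not by itself make pFBP comparable with Arm 1A, and the report should say so.

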2.14 Interim analysis

Primary endpoint: Objective Response Rate (ORR)

Part 1: Selection phase

The 1st interim analysis is planned once at least ten patients have been randomized into each of the three initial treatment combination arms, and have completed at least 20 weeks of treatment (corresponding to two post-baseline assessments) or discontinued the study. It is possible to terminate one or more combination arms at the 1st interim analyses for lack of adequate efficacy, i.e. futility. It is also possible for advance one or more combination arms at the 1st interim analysis to the expansion phase if those arms cross a specific efficacy probability threshold.

Assessment of futility and efficacy will be based on the calculated Bayesian predictive probabilities of occurrence, using the following criteria highlighted in [Table 2-9](#).

The (posterior) predictive distribution of future responders conditioned on the observed data at the interim is a beta-binomial distribution. More details on the (posterior) predictive distribution used for this study are highlighted in [Section 2.5.2](#).

Enrollment and assessment at subsequent interim analyses for each treatment group will continue at an assessment period as defined in Section 4.2 of the protocol, or 45 subjects have been randomized into a treatment group rules presented in [Section 2.5.2](#).

Note: If new combination arms are added to the study, those combination arms will have their interim analyses at the same time-points as the first three combination arms on this study (after 10 patients have been randomized and have sufficient data for analysis, and then if needed, at an assessment period as defined in Section 4.2 of the protocol, or 45 patients have been randomized into each arm).

Part 2: Expansion phase

No formal interim analysis is planned for this part of the trial. The primary analysis will be performed once the expanded arm has fully enrolled and also after all patients randomized in the expansion phase had at least 9 months of follow-up. This timing would allow for a potential minimum duration of response of 6 months for all subjects randomized. Formal

hypothesis testing of the primary endpoint (as described in [Section 2.5.2](#)) will be performed at the primary analysis. The final analysis will be performed at the end of the study as described in [Section 2.5.1](#).

3 Sample size calculation

In this section, sample size will be presented based on specific potential scenarios for true ORR. In particular, for selection phase (part 1), since one can consider a wide variety of potential true ORR scenarios, the sample size will not be based on an exact calculation leading to one fixed number, but will instead be characterized by simulation based on average number of subjects enrolled into these arms under each individual scenario for true ORR. It is important to emphasize that the true underlying efficacy activity (in terms of ORR) of the three initial arms will have a substantial bearing on the total sample size needed in part 1. Subsequently, and given the adaptive nature of the study design, the sample size needed in expansion phase (part 2) to ensure sufficient power will depend on the ORR observed in part 1 and in particular on the rate observed in the arm that qualifies for expansion to part 2.

The sample size calculation for parts 1 and 2 were performed using SAS 9.4 software, based on the probabilities of first determining a efficacious treatment and a futile (non-efficacious) treatment in the selection phase (part 1), and then determining the number of subjects needed to reject the null hypothesis (part 2). Assumptions and sample size calculations for both the selection and expansion phases are summarized in Section 10.8 of the protocol. Additional simulation results for both the selection and expansion phases will be summarized in the [\[SAP Technical Appendix\]](#).

4 Change to protocol specified analyses

The only changes to protocol specified analysis in the SAP is the inclusion of an IG analysis set for immunogenicity analysis, as well as specific sub-group analyses for efficacy and safety analysis.

5 Appendix

